Given this train of evidence, we are proposing a small, exploratory clinical trial investigating the role of VC in PSC. The trial will be conducted by investigators with long careers dedicated to the study of PSC and other hepatobiliary disorders. The trial will be executed at two sites that are both tertiary referral centers for PSC.

I. Goal:

The overall goal of this study is to examine the safety, tolerability, and efficacy of daily dosing with vidofludimus calcium over a 6-month period on the clinical course and progression of primary sclerosing cholangitis.

The results will help us:

- Establish proof-of-concept that VC may show activity for the treatment of PSC
- Gain insight into the effect of VC on profiles of the proinflammatory cytokines IL-17 and IFN γ
- Establish data to design more comprehensive clinical studies

II. Impact of Study:

This open-label, single-arm pilot study will give us the opportunity to explore the potential of this novel drug to show activity in patients suffering from PSC, a rare but devastating disease with no known effective treatment.

III. Expected Outcome:

We hypothesize that in PSC, daily treatment with vidofludimus calcium will result in reduction of serum ALP, a surrogate marker that has been shown to strongly correlate with positive outcomes in PSC. Further, we hypothesize that treatment will result in a decrease in certain proinflammatory cytokines, particularly IL-17 and IFN γ . We expect based on a wealth of preclinical and clinical evidence that treatment with vidofludimus calcium will be safe and well tolerated.

IV. Specific Aims of the Study:

1. Determine if VC reduces serum alkaline phosphatase (ALP) in adults with PSC. Levels of serum ALP after 3 and 6 months of VC treatment will be compared with baseline (month 0).
2. Assess other liver biochemistries (an indication of general liver health) at 3 and 6 months of VC treatment and compare to baseline (month 0).
3. Determine if changes in the proinflammatory cytokines IL-17 and IFN γ predict

response to VC. Cytokines will be measured at baseline, 4 weeks, and 6 months.

If successful, this low-risk, high-reward study will lay the groundwork for larger, more comprehensive clinical studies investigating the efficacy of VC in PSC. This could ultimately lead to the development of a successful therapy for PSC and significantly improve patient outcome and quality of life.

RESEARCH STRATEGY

Significance

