These results will help us:

- Establish feasibility of the hypothesis that VC will play a therapeutic role in treatment of PSC
- Gain insight into the effect of VC on profiles of the proinflammatory cytokines IL-17 and IFNy
- Pave the way for more comprehensive clinical studies

Study Design and Methodology

This pilot study will be a 6-month, 30-subject clinical trial to assess the effects of VC on a surrogate biochemical endpoint known to have relevant association with clinical outcomes in PSC. All endpoint tests chosen are rapid, inexpensive, and minimally invasive. Due to the low prevalence of PSC, the study will be a single-arm, open-label study. The study will be undertaken at two sites, Mayo Clinic, Rochester, Minnesota (20 subjects) and Mayo Clinic, Phoenix, Arizona (10 subjects), both of which are tertiary referral centers for PSC. Immunic AG, a biotechnology company based in Munich, Germany, will supply the study agent in sufficient quantities for the study (see Letter of Support from Immunic AG). We have confirmed through consultation with NIH personnel that this is permissible under this funding opportunity.

During the 6-month treatment period, subjects will receive 30 mg VC orally once daily, a dose determined to be both safe and therapeutically relevant based on previous clinical studies (see Table 1). This will be preceded by a lead-in dosing period where subjects will receive 15 mg VC once daily for 1 week. Lead-in dosing is used to minimize the risk of drug intolerance during the initial treatment period. While no clinically relevant adverse events have been noted at 30 mg once daily dosing, in rare instances potentially drug-related hematuria has been observed in the first few days of treatment at higher doses (≥ 70 mg/day). As a precaution, subjects will be monitored for two weeks after initial drug

exposure for elevated erythrocytes in the urine by a dipstick test. It is not anticipated that hematuria will be seen if it has not developed within the first two weeks of drug exposure.

The following endpoints will be assessed at various times during the study and compared with baseline:

- i. Primary endpoint:
 - a. Improvement of serum alkaline phosphatase (ALP) [baseline, 3 months, and 6 months]
- ii. Secondary endpoints:
 - a. Bilirubin, Total and Direct [baseline, 3 months and 6months]
 - b. AST and ALT (aspartate and alanine transaminases) [baseline, 3 months, and 6 months]

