Due to the relatively low prevalence, it is possible that 30 subjects meeting inclusion criteria cannot be recruited within the planned 6-month recruitment period or that they are not split roughly equally between the two sites. In that case, we will extend the recruitment period and if required, we will execute the study with as few as 20 subjects, regardless of the distribution between sites. After the study is complete, further research may reveal other potentially interesting biomarkers that should be examined and thus we have included storage of extra blood draws during the study. Given the pilot nature of this study, it is possible that benefits are seen even though results are not conclusive. Study data may be examined more carefully to determine if benefits occur in a distinct subpopulation of subjects (e.g. in PSC patients with UC versus those without).

Overall, considering the known safety data, the implemented risk minimization measures, the expected benefits in the target population, and the unmet medical need for treatment in PSC, the risk-benefit evaluation is considered favorable.

PROTECTION OF HUMAN SUBJECTS

This Human Subjects Research meets the definition of a clinical trial.

I. Risks to Human Subjects

a) Human Subjects Involvement, Characteristics, and Design: A total of 30 adults (age range 18-75 years) who meet the criteria for diagnosis of primary sclerosing cholangitis (PSC), as defined by the American Association for the Study of Liver Diseases (AASLD) published guidelines, will be enrolled into this study from two centers. PSC patients with and without inflammatory bowel disease (IBD) will be included. Other inclusion and exclusion criteria are detailed below:

Inclusion Criteria

- a. Male or female subject age 18-75 years
- b. Diagnosis of PSC consistent with the guidelines published by the AASLD. All subjects must have an elevated serum ALP of at least 1.5 times upper limit of normal (ULN) at baseline plus cholangiographic evidence of PSC (MRI, endoscopic retrograde cholangiography, or direct cholangiography).
- c. Indirect bilirubin <1.2 times the ULN
- d. An ultrasound (or equivalent imaging modality) that excludes biliary obstruction and malignancy within 6 months of study enrollment
- e. PSC with or without inflammatory bowel disease, such as ulcerative colitis or Crohn's disease
- f. Must agree to comply with the study protocol and provide informed consent

Exclusion Criteria

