b) Sources of Materials: Please refer to Table 3 for details on the data that will be collected from study subjects. Each study subject will be assigned a study identification number. No protected health information (PHI) will be collected. Blood samples, collected and stored at the respective research sites, will be labeled using the subject's unique study identification numbers. Study documents and generated data will be stored securely in a password-protected database and in locked cabinets in locked offices. Only research team members authorized by the principal investigator will have access to study subject's data.

Table 3 – Data Collection Schedule

	Screening ^a	Enrollment/ Baseline ^a	Lead-in Dosing Period	Treatment Period								Follow-up Period	
				Up to Month -1	Day 0	Week 1 ± 1d	W2 (D14) ± 3d	W4 ± 7d	W8 ± 7d	W12 [M3] ± 7d	W16 ± 7d	W20 ± 7d	W24 [M6] ± 7d
Procedures													
Informed Consent	x												
CLINICAL													
Demographics	x												
Medical History, initial	x												
Review inclusion and exclusion criteria	x	x											
Clinic Visit			x									x	
Physical Examination			x									x	
Vital signs			x									x	
MRCP (images from medical record) ^b			x									x	
Transient elastography (from medical record) ^b			x									x	
Telephone evaluations	x				x	x	x	x	x	x	x	x	
Review any concurrent medications	x	x			x	x	x	x	x	x	x	x	
Assess for PSC-related complications	x	x			x	x	x	x	x	x	x	x	
Assess for IBD-related symptoms or complications	x	x			x	x	x	x	x	x	x	x	
Adherence to study protocol					x	x	x	x	x	x	x	x	
Adverse events evaluation					x	x	x	x	x	x	x	x	
Dispense Study Medication		x ^c											
LABORATORY													
Hematuria testing by urine dipstick (patient self- administered every other day during lead-in period and during first week of Treatment				x	x								
HepBsAg, , Anti-HCV (from medical record)	x ^d												
HepBcAb, Anti-HAVIgM, (only if available from medical record)	x												
Screening for HIV and TB	x												
Creatinine with Estimated GFR (from medical record)	x												
Uric acid	x												
Urine pregnancy testing (Monthly during treatment period for women of child-bearing potential)	x	x			x	x	x	x	x	x			
Pharmacokinetics, if possible for those experiencing SAE						x							
ALP		x		x	x	x	x	x	x	x	x	x	
Bilirubin, Total and Direct/Indirect		x		x	x	x	x	x	x	x	x	x	
AST/ALT		x		x	x	x	x	x	x	x	x	x	
Blood sample collection for potential future analysis frozen at -70°C		x		x			x		x		x		

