Risks associated with the use of VC include hematuria early in the course of treatment, believed to be due to microcrystallization of excess uric acid in the urine. As a precaution against this risk, patients with serum uric acid levels >1.2 ULN will be excluded from the study. Additionally, study subjects will be advised to drink sufficient fluids during the study to ensure adequate urine flow. Further, the trial will include a one week lead-in period where subjects receive half the treatment dose to minimize the risk of drug intolerance during the initial treatment period. Subjects will be monitored for two weeks after initial drug exposure for elevated RBCs in the urine by a urine dipstick test. It is not anticipated that hematuria will be seen if it has not developed within the first two weeks of drug exposure. Positive results will be immediately reported to the study coordinator and standard medical care will be provided. Three consecutive positive readings will require microscopic assessment of urine for sediment. All findings of RBCs in the urine will be listed as urinalysis abnormalities but will only be recorded as an adverse event when deemed by the investigator to be clinically significant. The investigator will assess whether there are more probable alternatives to explain this finding (e.g. evidence of contamination, evidence of infection not considered secondary to a drug induced damage, other benign causes such as menstruation, vigorous exercise, viral illness, trauma, or infection). If moderate or severe hematuria (see Table 4) cannot be remedied, the subject will discontinue VC treatment.

Due to an occurrence of a potentially drug-related adverse event of hepatitis in a subject with Gilbert syndrome, patients with known or suspected Gilbert syndrome or with elevation of indirect (unconjugated) bilirubin above 1.2 ULN will be excluded from this clinical study

To protect pregnant women, fetuses, and breastfeeding children, women who are pregnant, attempting to become pregnant, or breastfeeding will be excluded from the study. For female subjects of childbearing age, some form of contraception will be required during the study. A urine pregnancy test will be performed during each clinic visit and once a month during the entire treatment period. Subjects with a positive pregnancy test will discontinue the study immediately.

Classification	Symptoms
Mild	Asymptomatic hematuria: clinical or diagnostic observations only

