- Elevated total bilirubin $\geq 2 \times$ baseline that does not return to within 10% of baseline within two weeks
- Serious allergic reaction
- Pregnancy or breastfeeding

Non-adherence to the study protocol by a study subject may, at the discretion of the principal investigator, be grounds for termination.

Statistical Analysis Plan: The proportion of patients with normalization of serum ALP at 3 months and 6 months and their corresponding confidence intervals will be estimated using exact binomial method. The primary endpoint is ALP normalization (within the normal limits of the laboratory test) rate at 6 months. We will define success as a 95% CI that does not overlap 0 at 6 months. Further, we will further investigate if the absolute ALP decreases over time using mixed model with repeated measures to account for within patient correlation over time.

All the liver biochemistries and proinflammatory cytokine profile over time will be analyzed using mixed model with repeated measures to investigate how VC treatment plays a role over the 6 months duration. The liver biochemistries and proinflammatory cytokine will be dichotomized into abnormal and normal groups if possible and further the abnormal proportions at different time points will be estimated to see the trend over time.

The incidence, type and relatedness of serious adverse events and adverse events will be monitored and reported for all the subjects.

Adherence to Regulatory Standards: The investigators will ensure that this study is conducted in full conformity with Regulations for the Protection of Human Subjects of Research codified in 45 CFR Part 46, 21 CFR Part 50, 21 CFR part 56, and the ICH; Good Clinical Practice E6.

ClinicalTrials.gov Requirements: The principal investigator will ensure that this clinical trial is properly registered at www.clinicaltrials.gov, per the Public Law 110-85 (also known as the FDA Amendments Act (FDAAA) of 2007), no later than 21 days after the first subject is enrolled. The principal investigator will also ensure that the results (including adverse events) of this clinical trial are reported no later than 1 year after completion of the clinical trial.

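### No urine dipstick is planned before the first dose and only adverse events are summarised, so the reported hematuria rate rests on undefined investigator discretion and cannot separate new from pre-existing hematuria.

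*Combined protocol and SAP*

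**What the plan says.** **Design.** Under Impact of Study: "This open-label, single-arm pilot study will give us the opportunity to explore the potential of this novel drug". Under Study Design and Methodology: "This pilot study will be a 6-month, 30-subject clinical trial". Under Risk Mitigation and Alternative Strategies, if recruitment is slow: "we will execute the study with as few as 20 subjects".

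**Timing of the dipstick.** Section II.b.1 (protections against study-drug risks): "Subjects will be monitored for two weeks after initial drug exposure for elevated RBCs in the urine by a urine dipstick test". The Table 3 row describes the test as self-"administered every other day during lead-in period and during first week of Treatment". Study Design and Methodology and Timeline and Schedule give the same two-week window, the latter with the alternate-day frequency. Table 3 has no urinalysis row at screening or baseline; the only urine test there is for pregnancy. Hematuria at entry is not an exclusion criterion.

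**Recording.** Section II.b.1 lists all red-cell findings as urinalysis abnormalities, then says that they "will only be recorded as an adverse event when deemed by the investigator to be clinically significant". The investigator weighs other explanations such as contamination, infection, menstruation or exercise, and three positives in a row lead to microscopy. The Data and Safety Monitoring Plan adds that safety information of every level goes into the clinical database.

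**Grading.** Table 4 defines Mild as "Asymptomatic hematuria: clinical or diagnostic observations only". CTCAE grade 1 in Table 6 likewise covers findings without symptoms.

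**Analysis.** The only safety sentence in the Statistical Analysis Plan is: "The incidence, type and relatedness of serious adverse events and adverse events will be monitored and reported for all the subjects". It mentions no summary of dipstick or urinalysis results.

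**The concern.** Safety and tolerability are part of the stated goal, and the results are meant to inform the design of later studies. Hematuria is the first entry in Table 7 and the drug-related risk that eligible subjects are actively tested for. Two features weaken what the trial can report about it.

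First, with no control arm, a subject's own pre-dose value is the only reference available, and none is taken. Section II.b.1 uses that reference for the liver: the multiples of ALP, AST, ALT and total bilirubin that trigger further testing are all set against baseline. The investigator who has to decide whether a positive strip has another cause has no such value.

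Second, the planned summary counts adverse events, and whether a positive strip becomes one turns on an undefined criterion applied at two sites. The same finding could be counted at one site and not at the other. A reader of the final report could not tell a low rate of hematuria from a strict use of the criterion.

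**Working it through.** The plan states no hematuria rate, precision target or safety sample size, so there is no figure to reproduce. The point rests on tracing one positive strip through the text; the arithmetic only illustrates scale.

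**Step 1: is there a pre-dose reading?** Study Design and Methodology, Timeline and Schedule, section II.b.1 and the Table 3 row label agree that testing covers the lead-in week and the first treatment week. The Table 3 columns are broken in the text available, but the row label and the prose settle the timing. There is no pre-dose reading.

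**Step 2: where does a positive strip go?** It goes to the coordinator, to the urinalysis listing and to the database. It becomes an adverse event only if the investigator considers it clinically significant. Only adverse events reach a planned summary. A positive strip can therefore be fully documented and still appear in no planned result.

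**Step 3: subjects already positive before dosing (assumed rates).** Let p be the share of subjects persistently positive before the first tablet. Expected number = np, and P(at least one) = 1 − (1 − p)^n, with n = 30 (planned) or 20 (minimum).

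| p (assumed) | Expected of 30 | P(≥1 of 30) | Expected of 20 | P(≥1 of 20) |
|---|---|---|---|---|
| 2% | 0.6 | 45% | 0.4 | 33% |
| 5% | 1.5 | 79% | 1.0 | 64% |
| 10% | 3.0 | 96% | 2.0 | 88% |
| 20% | 6.0 | 99.9% | 4.0 | 99% |

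These subjects would test positive on drug with no drug effect.

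**Step 4: intermittent positives (assumed rates).** Alternate-day testing over 14 days gives about 7 readings. If each has an independent chance q of being positive without drug effect, P(any positive) = 1 − (1 − q)^7.

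- q = 1%: 6.8% of subjects, or 2.0 of 30.
- q = 2%: 13.2%, or 4.0 of 30.
- q = 5%: 30.2%, or 9.0 of 30.

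A single pre-dose strip would not remove this component.

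**Step 5: effect of the recording rule (assumed count).** Suppose 6 of 30 subjects have a positive strip: 20%, exact 95% CI 7.7% to 38.6%.

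- None considered clinically significant: 0/30 = 0%, exact 95% upper limit 1 − 0.025^(1/30) = 11.6%. With 20 subjects, the upper limit for 0/20 is 16.8%.
- Three considered significant: 3/30 = 10%, CI 2.1% to 26.5%.
- All six: 6/30 = 20%.

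The same strips give 0% to 20%. With 0/30 recorded, the upper limit of 11.6% lies below the 20% that the strips showed. That interval describes recorded adverse events, not hematuria.

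**The case against.** The protocol presents hematuria as unlikely at the trial dose. It calls the monitoring a precaution, places earlier cases at higher doses, and reports no excess over placebo below 70 mg daily. Subjects with raised serum uric acid are excluded, positives are reported at once, repeated positives go to microscopy, and an independent board addresses adverse event reports. The trial is an exploratory pilot in which no hypothesis or sample size depends on hematuria. The Statistical Analysis Plan does not forbid further summaries. All of this stands, and it limits the weight of the point.

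Several stronger readings are tempting, but the documents do not support them:

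- **That positive findings are lost.** They are listed and entered in the database. What is missing is a planned summary.
- **That hematuria is the only drug effect expected.** Table 7 also lists complications of Gilbert syndrome, and the Potential Risks section describes hepatitis in a subject with that syndrome and biliary hyperplasia in animals.
- **That Tables 4 and 6 contradict the recording rule.** Both can be read as severity scales, with section II.b.1 deciding what counts as an adverse event. The link is unstated, which is less than a contradiction.
- **That no finding can be attributed at all.** Alternative causes are weighed and microscopy is available. The judgement simply lacks a pre-dose value.
- **That the probabilities in Step 3 measure bias.** They give the chance of at least one pre-existing positive at an assumed rate. Such a subject enters the adverse event count only if the finding is considered clinically significant.

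None of this supplies a pre-dose reading or a planned table.

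**Conclusion.** The point holds as a moderate gap in safety data collection and reporting. As planned, the hematuria adverse event rate depends on how each investigator applies an undefined criterion, and hematuria present before dosing cannot be told from new hematuria.

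The size cannot be fixed from the documents, because they give no background positivity rate. At assumed pre-dose rates of 2% to 10%, 0.6 to 3 of 30 subjects would test positive without drug effect. With an assumed 6 of 30 positive, the recorded rate could be anything from 0% to 20%. The error can run either way: pre-existing hematuria may be counted as an event on drug, and new asymptomatic hematuria may go unsummarised.

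A reader should not infer that a baseline strip would make new positives attributable to the drug. It detects hematuria present that day; it does not exclude intermittent causes or replace a control arm. The primary endpoint is not affected.

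**What to change.** 1. **Table 3:** add one dipstick at baseline, before the first tablet, using the same kit as the later readings. A baseline clinic visit already exists. If medication is mailed afterwards, as the table notes appear to allow, the strip can be done at home before the first tablet.
2. **Statistical Analysis Plan:** tabulate the number of subjects with any positive reading, with a new positive (negative before dosing) and with three consecutive positives. Show each for the lead-in week and the first full-dose week, with exact 95% CIs and the number of readings done, whether or not an adverse event was recorded. State how a run of positives that crosses the two weeks is counted. Place the table beside the adverse event rate.
3. **Section II.b.1:** define clinical significance for this purpose, and state how the recording rule relates to Mild in Table 4 and to CTCAE grade 1.

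The cost is one strip per subject (20 to 30 in all), one table of data that are otherwise already collected, and a clarifying sentence or two. The reported hematuria frequency may look less favourable. No dose or treatment rule changes.

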- a. Pregnancy, attempting to become pregnant, or breastfeeding
- b. Active hepatitis A or B infection
- c. Active hepatitis C infection (antibody positive); patients with a history of hepatitis C infection will be eligible for this study if they have undetectable levels of HCV RNA
- d. HIV/AIDS (per medical record or HIVAb/HIV antigen), tuberculosis, or positive interferon-gamma assay (IGRAs) for *Mycobacterium tuberculosis*
- e. Other cholestatic liver disease such as primary biliary cholangitis and cholestatic diseases of pregnancy
- f. History of metabolic liver diseases such as Wilson's disease, Gilbert's syndrome or hemochromatosis

- g. Serum uric acid levels at Screening >1.2 ULN
- h. Inherited diseases of the liver such as α -1 antitrypsin deficiency
- i. Immunoglobulin G4-related cholangitis
- j. PSC with concomitant autoimmune hepatitis (AIH) and/or primary biliary cholangitis
- k. Secondary sclerosing cholangitis (SSC)
- l. Active acute ascending cholangitis requiring antibiotics
- m. CCA (malignant biliary stricture, neoplasm, and cytology/histopathology or positive fluorescence in situ hybridization (FISH) consistent with adenocarcinoma of the bile duct)
- n. A liver biopsy, if one has been previously obtained, which showed non-alcoholic steatohepatitis (NASH). Patients with suspected fatty liver by imaging will not be excluded.
- o. Presence of complications of advanced PSC such as hepatic encephalopathy, portal hypertension, hepato-renal syndrome, and hepato-pulmonary syndrome
- p. History of liver transplantation, anticipated need for liver transplantation within 12 months from randomization, a Model of End-stage Liver Disease (MELD) score of ≥ 15 , or a Child Pugh score > 6
- q. Ongoing alcohol abuse (> 4 drinks per day for men, and > 2 drinks per day for women)
- r. Moderate-to-severe renal impairment with a calculated creatinine clearance of < 60 mL/min
- s. Any other conditions or abnormalities that, in the opinion of the investigator, may compromise the safety of the subject or interfere with the subject participating in or completing the study
- t. Evidence of, or treatment for, *C. difficile* infection within 30 days before the initiation of the study drug
- u. Evidence of active *C. difficile* infection during the screening phase confirmed by a positive *C. difficile* toxin B
- v. Subjects who have been treated for intestinal pathogens other than *C. difficile* infection within 30 days prior to study drug initiation

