Moderate	Symptomatic hematuria: with moderate flank pain (and including short-term [treatment for <24 hours], standard dose therapy with oral nonsteroidal anti-inflammatory drugs, oral acetaminophen or oral aspirin), interfering with but not limiting activities of daily living
Severe	Gross or macrohematuria; Any hematuria in connection with severe flank pain limiting activities of daily living. Any hematuria requiring additional treatment (e.g. oral anti-emetics or muscle relaxants, around the clock narcotic analgesics, use of narcotics or any intravenous treatment) or procedures for maintaining adequate urinary flow (e.g. urinary catheter or bladder irrigation).

Table 4. Classification of symptoms of hematuria

To date, no clear indication for drug-induced hepatic effects has been identified in clinical trials with vidofludimus. Nevertheless, liver function monitoring (ALP, AST, ALT and bilirubin) will be included as part of this clinical trial. Further liver function testing will be initiated in the event of any of the following:

- a. Elevated ALP $\geq 3 \times$ baseline
- b. Elevated AST and/or ALT $\geq 3 \times$ baseline
- c. Elevated total bilirubin $\geq 2 \times$ baseline
- d. Any elevation of bilirubin of 0.3mg/dl or more, regardless of ALT or AST levels, and in the presence of indicators of immunological reaction (e.g. rash or $>5\%$ eosinophilia), or appearance of nausea, vomiting, and right upper quadrant pain (symptoms consistent with clinical hepatitis)
- e. other suspected drug-induced liver injury(DILI)

Testing of all liver parameters (ALP, ALT, AST, total and indirect bilirubin) will be repeated within 48 to 72 hours. If repeat testing still shows an elevated liver function test, the patient will be placed under close observation, as defined in the DILI guidance, until the liver enzymes return to within 10% of baseline. This includes, but is not limited to, repeating liver function tests 2 or 3 times weekly, detailed evaluation of medical history and concomitant drug use, ruling out other causes of liver enzyme increases, and further liver function tests as considered appropriate by the investigator.

Table 5 – Algorithm for monitoring and interrupting study drug for Hepatocellular DILI signals in clinical trials evaluating drugs for patients with PBC and PSC without advance cirrhosis^a and Normal Baseline ALT Values (Palmer et al 2019)

Treatment emergent ALT	Bilirubin	Symptoms ^b	Action

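### The only explicit instructions to interrupt study drug for a liver signal (Table 5) are titled for normal baseline ALT, yet eligibility admits subjects with raised ALT

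*Combined protocol and SAP*

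**What the plan says.** The liver-safety text is in Protection of Human Subjects, under Protections Against Risk (study drug).

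- **Triggers for all subjects.** Further liver testing starts at ALP, AST or ALT of at least 3 x baseline, at total bilirubin of at least 2 x baseline, at a smaller bilirubin rise with immunological signs or hepatitis-type symptoms, or under a catch-all, "other suspected drug-induced liver injury(DILI)".
- **Action on a trigger.** "Testing of all liver parameters (ALP, ALT, AST, total and indirect bilirubin) will be repeated within 48 to 72 hours". If a value is still elevated, the subject is "placed under close observation, as defined in the DILI guidance, until the liver enzymes return to within 10% of baseline". This includes liver tests two or three times weekly and a search for other causes. The guidance is not identified.
- **Table 5.** The title scopes it to "clinical trials evaluating drugs for patients with PBC and PSC without advance cirrhosis^a and Normal Baseline ALT Values". The first column is headed "Treatment emergent ALT". Drug is interrupted at ALT of at least 8 x ULN; at 3 x ULN with total bilirubin of at least 2 x baseline; and at 5 x ULN with symptoms. At 5 x ULN with normal bilirubin and no symptoms, tests are repeated in 2 to 5 days.
- **After Table 5.** Two sentences limit restarting the drug and require discontinuation if an elevation recurs on re-challenge.
- **Individual termination (Data and Safety Monitoring Plan).** Participation ends if ALP, AST or ALT of at least 3 x baseline, or total bilirubin of at least 2 x baseline, is not back within 10% of baseline in two weeks.
- **Eligibility.** "All subjects must have an elevated serum ALP of at least 1.5 times upper limit of normal (ULN) at baseline". Indirect bilirubin, MELD and Child Pugh are also limited. ALT and AST are not. Exclusion criterion n adds: "Patients with suspected fatty liver by imaging will not be excluded".

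**The concern.** The hold algorithm is written for a population narrower than the one that can enrol, and no sentence says whether the title restricts its use in this trial. The title may simply have come over with the table. It names PBC, yet the exclusions include "Other cholestatic liver disease such as primary biliary cholangitis and cholestatic diseases of pregnancy". The rows also provide for Gilbert's syndrome, which is excluded too. A site cannot tell from the text whether the normal-ALT condition is equally incidental.

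What is at stake is the interval between a confirmed signal and termination. If the title is taken at its word, a subject with raised baseline ALT who develops a combined ALT and bilirubin rise, or an ALT rise with symptoms, is retested and watched closely, but nothing visible tells the site to stop dosing meanwhile. The two sites could also handle the same result differently, one interrupting drug and the other observing on drug.

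**Working it through.** The protocol gives no figure to reproduce here. The check sets the rules side by side and converts between the two scales.

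**Inputs from the documents:** Table 5 thresholds of 3, 5 and 8 x ULN; the all-subject ALT trigger of 3 x baseline; the bilirubin trigger of 2 x baseline; the two-week termination window.

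**Assumed:** baseline ALT of 1.5, 2 or 3 x ULN, for illustration. The documents give no baseline ALT distribution.

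**Step 1. Can raised ALT enrol?** The inclusion and exclusion criteria contain no ALT or AST limit, so yes. The cirrhosis part of Table 5's title raises no conflict, because Child Pugh above 6 is excluded.

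**Step 2. Same clinical signal, two baselines, table read as titled.**

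| Signal | Normal baseline ALT | Raised baseline ALT |
|---|---|---|
| ALT rise with total bilirubin at least 2 x baseline | Interrupt at ALT 3 x ULN | At ALT 3 x baseline: retest in 48–72 h, close observation, termination if not recovered in two weeks; no hold stated |
| ALT rise with symptoms | Interrupt at ALT 5 x ULN | Same pathway; no hold stated |

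For example, with baseline 2 x ULN, ALT of 3 x 2 = 6 x ULN and doubled bilirubin meets both the ALT and the bilirubin trigger. Dosing is not addressed until the two-week termination rule. The restart and re-challenge sentences presuppose a hold, but nothing visible starts one for this subject.

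**Step 3. Conversion of scales.** Trigger in ULN units = 3 x baseline. Table 5's top threshold as a multiple of baseline = 8 / baseline.

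| Baseline ALT (x ULN) | 3 x baseline, in ULN | 8 x ULN, as multiple of baseline |
|---|---|---|
| 1 | 3 | 8.00 |
| 1.5 | 4.5 | 5.33 |
| 2 | 6 | 4.00 |
| 3 | 9 | 2.67 |

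The two are equal at a baseline of 8 / 3 = 2.67 x ULN. Above that, read as titled, ALT of 8 x ULN does not reach even the numeric ALT retest trigger. At baseline 3 x ULN it is 2.67 x baseline against a trigger of 9 x ULN. With stable bilirubin and no other trigger, only the catch-all for suspected liver injury could apply. From a normal baseline, the same ALT value means interruption whatever the bilirubin or symptoms.

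**The case against.** The strongest reply is that subjects with raised ALT are well covered. The 3 x baseline triggers, the retest, the two-to-three-times-weekly monitoring and the termination rule apply whatever the baseline. The restart condition after Table 5 uses the same 10%-of-baseline wording as the all-subject pathway, and the re-challenge rule covers ALP, AST and bilirubin as well as ALT, so a hold may be understood there. The DILI guidance may state one. Investigators can hold drug on judgement, laboratory tests are scheduled every four weeks, and an independent DSMB with cholestatic-disease experience is in place. The protocol reports no clear hepatic signal, and the one hepatitis SAE was in a subject with Gilbert syndrome, now excluded. Several causes of raised ALT are excluded too: autoimmune hepatitis, NASH on biopsy, active viral hepatitis, metabolic liver disease and alcohol abuse.

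Most of this stands, and it limits the size of the point. It does not supply the missing instruction. The restart sentences imply a hold without saying when it begins, and the guidance cannot be checked.

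Three stronger inferences are tempting but unsupported:

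- *That subjects with raised baseline ALT have no stopping rule, or are merely retested.* Close observation and two-week termination apply to them. These criteria also largely meet the protocol's stated intention to include discontinuation criteria.
- *That applying Table 5 to everyone would hold subjects at entry.* At baseline 3 x ULN the ALT part of the bilirubin row is numerically met, but the row also needs total bilirubin of at least 2 x baseline.
- *That applying Table 5 to everyone would make holding precede any retest.* The 5 x ULN row already calls for repeat tests before the 8 x ULN hold when bilirubin is normal and there are no symptoms.

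**Conclusion.** The point holds as a gap in the hold instruction, not as an absence of liver stopping rules. Read as titled, the protocol gives no visible trigger to interrupt drug in an eligible subject with raised baseline ALT, even with ALT of at least 3 x baseline plus doubled total bilirubin or symptoms. What separates these subjects from those with normal baseline ALT is immediate interruption versus close observation, with termination only if values have not recovered within two weeks.

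The conclusion rests on taking the title literally, which the text neither confirms nor rules out, and on the unseen guidance containing no hold rule. The 2 and 3 x ULN baselines are illustrative, the number of subjects affected is unknown, and no harm is demonstrated. It should be fixed because it concerns a safety instruction and the correction is cheap.

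**What to change.** 1. State in one sentence that Table 5 applies to subjects with normal baseline ALT.
2. Add a row for baseline ALT above ULN: interrupt drug when ALT is at least 3 x baseline together with either total bilirubin of at least 2 x baseline or the symptoms in Table 5's footnote b. Apply Table 5's existing restart rules. Both numeric thresholds are already in the protocol.
3. Identify the DILI guidance. If it already has a hold rule for raised baseline ALT, cite that rule in place of the new row.

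The row does not address an isolated ALT rise from a raised baseline. The existing retest, observation and termination rules, the catch-all trigger and investigator judgement would continue to govern that case.

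The cost is amendment wording, site retraining and possibly a few more temporary holds. No new scheduled visits are needed.
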